6 STUDY CONDUCT AND DESCRIPTION OF STUDY PROCEDURES

6.1 Study Materials

The following study materials will be provided at the study start:

- Investigator File/Study Binder
- Pharmacy Binder
- Drug Accountability Logs
- Sample source documents, where applicable
- Concomitant medication paper diary (take home for subject)
- Investigator Brochure
- Interactive Web-based Response System (IWRS) manual
- Electronic Case Report Forms (eCRF) instructions
 - o Electronic Case Report Forms (eCRFs) will be prepared for all data collection fields
 - All sites will use an Electronic Data Capture (EDC) tool to submit study data to the CRO. Electronic Case Report Forms (eCRFs) will be prepared for all data collection fields including Serious Adverse Events (SAE) Reporting. SAE data (including queries) will be submitted to the CRO using eCRFs.
- Electronic Clinical Outcome Assessment (eCOA) Handheld devices (eDiary)
 - The eDiary will be used daily during the Observation Phase and DBT Phase to record migraine occurrence, migraine pain features and associated symptoms, use of acute migraine medication (i.e., triptans, ergotamine, or other). The eDiary will be used during the DBT phase to record select subject-rated scales (PoM and SM). Any assessment completed by the subject in the eDiary will be transferred from the site/subject to the vendor and from the vendor to the CRO and Sponsor. No additional source documents are required for scales and assessments completed by the subject on the eDiary. In the OLE Phase, the PoM and SM will be reported on paper forms at the site.
- Laboratory kits and laboratory manual
 - Safety laboratory, plasma, urinalysis and serum instructions for all specimens collected will be provided by a designated central laboratory.
- ECG Machine and instructions

- ECG equipment, supplies, instructions and training materials will be supplied by a centralized ECG vendor.
- SAE forms and SAE Reporting instructions
- Pregnancy surveillance forms
- C-SSRS documents
- MIDAS forms
- MSQ v 2.1 forms
- PoM forms (OLE Phase only)
- SM forms (OLE Phase only)
- CGI-c forms
- Study system access:
 - o Electronic Data Capture (EDC) tool to submit study data to Sponsor / CRO
 - o IWRS
 - Central Laboratory
 - Central ECG Vendor

6.2 Safety Assessments

6.2.1 Vital Signs and Physical Measurements (Height and Weight)

Vital signs, body weight and height will be recorded at the scheduled visits as outlined in Table 1.

6.2.2 Electrocardiogram (ECG)

A standard 12-lead ECG will be recorded during the Observation Phase and at all scheduled visits as outlined in Table 1 and Table 2. A central ECG service will be utilized for all ECGs. The over-read from the central ECG vendor should be used to determine eligibility for the study. The investigator will determine whether any ECG abnormalities are clinically significant based on the overread from the central ECG vendor.

6.2.3 Physical Exam

Subjects will undergo a complete physical examination during the Observation Phase and brief and symptom-directed physical exam at all scheduled visits as outlined in Table 1 and Table 2. Targeted physical examinations to include examination of heart, abdomen, and lungs; plus review of any other system to be guided by signs and symptoms.

6.2.4 Laboratory Tests

The investigator must review the laboratory report, document this review, and record any clinically relevant changes occurring during the study in the AE section of the CRF. The laboratory reports must be filed with the source documents. Clinically significant abnormal laboratory test findings are those which are not associated with the underlying disease, unless judged by the investigator to be more severe than expected for the participant's condition.

6.2.4.1 Safety Laboratory Testing

Blood and urine samples will be obtained as outlined in Table 1 and Table 2 for clinical laboratory evaluations. A central laboratory vendor will be utilized for this study and a laboratory manual will be provided to each site. If possible, subjects should be fasting for a minimum of 8 hours before laboratory tests. However, if a subject is not fasting at a given visit, the blood draw should still be performed, and the non-fasting status should be documented

1. Clinical safety labs:

Hematology: Hemoglobin, hematocrit, red blood cell count, white blood cell count with differential, and platelets;

Chemistry: Sodium, potassium, chloride, bicarbonate, calcium; glucose, BUN (urea), serum creatinine, uric acid, LDH, total protein, albumin.

eGFR estimated using the MDRD formula (calculated at central lab).

- 2. **LFTs**: AST, ALT, Alkaline Phosphatase and Bilirubin (Total, Direct, Indirect), CK (fractionation will be ordered if CK result is > 5.0x ULN).
- 3. HbA1c
- 4. **Lipid panel:** Cholesterol, LDL, HDL, triglycerides.
- 5. **Urinalysis:** pH, specific gravity, ketones, nitrites, urobilinogen, leukocyte esterase, protein, glucose, and blood. If blood, protein or leukocytes are positive, reflex to microscopic examination.
- 6. **Urine Drug Screen:** For drugs of abuse.
- 7. **FSH:** At screening in female subjects to confirm postmenopausal status, if applicable.

Additional tests may be required to evaluate laboratory abnormalities and/or adverse events; please refer to the Laboratory Manual.

6.2.4.2 PK Testing

PK will be collected at the Week 4 and Week 8 Visits only. Subjects will be instructed to not take study drug until they are at the study site. Subjects will have PK drawn predose and at least 1 hour postdose. The time of dose administration in the clinic, time and date of last dose

and the exact time of PK sample collection will be documented at the clinic visit. Subjects should be fasting prior to dose administration (at least 4 hours after the last meal) and for duration of PK assessments.

6.2.4.3 Pregnancy Testing

WOCBP will complete pregnancy tests (serum and/or urine) at specified study visits, prior to taking study drug, and as outlined in Refer to Section 5.6.

6.2.5 Columbia-Suicide Severity Rating Scale (C-SSRS)

The Columbia-Suicide Severity Rating Scale (C-SSRS) is a questionnaire used for suicide Assessment.¹³ The C-SSRS "Screening version" will be used at the Screening Visit and the "Since Last Visit version" will be used at subsequent visits in this study.

The C-SSRS Assessment is intended to help establish a person's immediate risk of suicide. The C-SSRS is a clinician administered scale that should be administered by a certified rater. This scale will be collected on site with a paper form. The C-SSRS should be reviewed by the Investigator or designee before the subject is allowed to leave clinic.

At the Screening Visit, the recall period for completing is 12 months for suicidal ideation and 10 years for suicidal behavior; at all other visits, the recall period for completing the C-SSRS is since the last visit (reference Table 1 and Table 2).

If the Investigator determines that a participant is at risk of suicide or self-harm, or reports a "Yes" response to any question during the course of the study, appropriate measures to ensure the participant's safety and obtain mental health evaluation must be implemented. In such circumstances, the participant must immediately be discontinued from the study. The event should be recorded as either a non-serious AE or SAE through the Follow-up Week 8 Visit as determined by the Investigator and reported within 24 hours to the Sponsor.

6.3 Efficacy Assessments

The eDiary will be used daily to record acute migraine medication dosing occurrences and migraine pain features and associated symptoms during the Observation Phase and DBT Phase.

Efficacy assessments will be derived from eDiary data and will include the number of migraine days per month by pain intensity (total; moderate or severe), and number of acute migraine-specific medication days per month, in each month by study period.

6.4 Other Assessments

6.4.1 Migraine-Specific Quality of Life Questionnaire v 2.1

Impact of treatment on subject-reported quality of life will be assessed using the Migraine-Specific Qualify-of-Life Questionnaire version 2.1 (MSQ v 2.1). The MSQ v 2.1 is a 14-item instrument that has been validated in 3 domains: role function – restrictive, role function – preventive, and emotional function. ¹⁵ The MSQ will be completed on a paper form at the site.

6.4.2 Migraine Disability Assessment

The Migraine Disability Assessment (MIDAS) is a retrospective, subject-reported, 5-item questionnaire that measures headache-related disability as lost days due to headache from paid work or school, household work and non-work activities over a 3-month period. ¹⁶ The MIDAS will be completed on a paper form at the site.

6.4.3 Preference of Medication Scale

The Preference of Medication Scale (PoM) is a subject-rated, 5-point scale that measures preference of the study drug compared to the previous medications to treat migraine pain. The eDiary will be used to evaluate the PoM in the DBT Phase, and a paper form will be used at the site to evaluate the PoM in the OLE Phase.

6.4.4 Satisfaction with Medication Scale

The Satisfaction with Medication (SM) scale is a subject-rated, 7-point scale that measures satisfaction with the study drug to treat migraine headaches. The eDiary will be used to evaluate the SM in the DBT Phase, and a paper form will be used at the site to evaluate the SM in the OLE Phase.

6.4.5 Clinical Global Impression – Change (CGI-c) Scale

The Clinical Global Impression-change (CGI-c) scale is an observer-rated, 7-point scale that measures subject total improvement relative to the investigator's past experience with other subjects with the same diagnosis, with or without collateral information. ¹⁷ The CGI-c will be administered by the investigator or designee who has been trained on administration and will be completed on a paper form at the site.

6.5 Early Discontinuation from the Study

Subjects MUST discontinue investigational product (and non-investigational product at the discretion of the investigator) for any of the following reasons:

- Withdrawal of informed consent (subject's decision to withdraw for any reason)
- Any clinical adverse event (AE), laboratory abnormality or intercurrent illness which, in the opinion of the investigator or sponsor, indicates that continued participation in the study is not in the best interest of the subject
- Pregnancy
- Termination of the study by Biohaven Pharmaceuticals
- Loss of ability to freely provide consent through imprisonment or involuntary incarceration for treatment of either a psychiatric or physical (e.g., infectious disease) illness

- Poor compliance with study procedures and visits, including poor completion compliance with evening reports in eDiary; poor compliance with study drug – see Schedule of Assessments Table 1 and Table 2.
- All subjects who discontinue in the DBT Phase early should comply with protocol specified DBT EOT procedures as outlined in Table 1. All subjects who discontinue in the OLE Phase early should comply with the protocol specified OLE EOT procedures as outlined in Table 2. The only exception to this requirement is when a subject withdraws consent for all study procedures or loses the ability to consent freely (i.e., is imprisoned or involuntarily incarcerated for the treatment of either a psychiatric or physical illness).

6.5.1 Lost to Follow-up

A participant will be considered lost to follow-up if he or she repeatedly fails to return for scheduled visits and is unable to be contacted by the study site.

The following actions must be taken if a participant fails to return to the clinic for a required study visit:

- The site must attempt to contact the participant and reschedule the missed visit as soon as
 possible and counsel the participant on the importance of maintaining the assigned visit
 schedule and ascertain whether or not the participant wishes to and/or should continue in
 the study.
- Before a participant is deemed lost to follow-up, the investigator or designee must make
 every effort to regain contact with the participant (where possible, 3 telephone calls and,
 if necessary, a certified letter to the participant's last known mailing address or local
 equivalent methods). These contact attempts should be documented in the participant's
 medical record
- Should the participant continue to be unreachable, he/she will be considered to have withdrawn from the study.

6.6 Clinical Trial Subject Database (CTSdatabase)

CTSdatabase is a clinical trial subject registry that maintains the privacy and security of research subjects while providing sponsors and investigators with crucial information about subjects' current and/or previous study participation.

CTSdatabase has been shown to reduce the number of duplicate and professional subjects entering clinical trials.

The use of this database must be presented to all subjects participating in this protocol. If subjects refuse to provide authorization, the study team should be notified. At the time of providing the Informed Consent for the study, the Investigator or designee will explain the IRB-approved Subject Database Authorization to the subject and witness the signature.

During screening, site staff that have received training and login information should access www.ctsdatabase.com and enter the last 7 digits of the subject study ID and authorized subject identifiers. An immediate report detailing matches is generated and should be printed

for source documentation. The report will specify either (1) no matches found, (2) a match was found with a subject participating in another study within 30 days or (3) the subject matches with a subject who has *pre*-screened at another site.

At the last subject contact, CTSdatabase staff will automatically close out subjects (SF, ET or Completer) based on IWRS information.

7 STUDY DRUG MANAGEMENT

7.1 Description of Study Drug

7.1.1 Investigational Product

An investigational product, also known as investigational medicinal product in some regions, is defined as follows:

A pharmaceutical form of an active substance or placebo being tested or used as a reference in a clinical study, including products already with a marketing authorization but used or assembled (formulated or packaged) in a way different from the authorized form, or used for an unauthorized indication, or when used to gain further information about the authorized form.

The investigational product should be stored in a secure area according to local regulations. It is the responsibility of the investigator to ensure that investigational product is only dispensed to study subjects. The investigational product must be dispensed only from official study sites by authorized personnel according to local regulations.

In this protocol, investigational product (study drug) is zavegepant (BHV-3500) 25 mg soft gelatin capsule (SGC) or matching placebo.

7.1.2 Non-Investigational Product

In this protocol, there are no non-investigational products.

7.1.3 Formulation

Zavegepant (BHV-3500) is formulated as a 25 mg soft gelatin capsule (SGC) taken as either 4 soft gelatin capsules (SGC) for each 100 mg daily dose (25 mg x 4 = 100 mg) or 8 SCG for each 200 mg daily dose (25 mg x 8 = 200 mg).

7.1.4 Packaging, Shipment and Storage

The product storage manager should ensure that the study drug is stored in accordance with the environmental conditions (temperature, light, and humidity) as determined by the sponsor. Please see the Pharmacy Manual/Investigator Brochure for specific conditions. If concerns regarding the quality or appearance of the study drug arise, do not dispense the study drug and contact the sponsor/CRO immediately.

7.2 Dose and Administration

7.2.1 Method of Assigning Subject Identification

The Investigator or designee will need to access an Interactive Web-based Response System (IWRS) in order to register each subject. Initially, after informed consent is obtained at the Screening Visit, the Investigator or designee will enter the subject into the study and obtain a subject number assignment. At the Baseline Visit and subsequent visits in the DBT and OLE

Phases, container assignments will be obtained by the Investigator (or designee) via the IWRS system. This subject number must not be reused for any other participant in the study. Subjects will maintain their subject number assigned at screening, throughout the trial.

At the Baseline Visit, eligible subjects will be randomized to a treatment group (see Section 1.4.1). The randomization will be stratified by stable prophylactic migraine medication use through randomization (yes or no), as determined by site review of subjects' concomitant medication paper diary. Subjects should be categorized as "yes" if they took a specified prophylactic migraine medication > 3 months (12 weeks) before the Screening Visit and through randomization, i.e., (1) the medication start date is > 12 weeks before the Screening Visit date, **and** (2) either the medication stop date is on or after the randomization date or the medication is ongoing. Otherwise, subjects should be categorized as "no".

Subjects may not be rescreened for this study.

Study drug will be assigned via IWRS; the system will assign specific container numbers for all study drug to be dispensed to the subject. Sites will be responsible for recording the container numbers dispensed to the subject on the Drug Accountability Form provided in the Study Binder, as well as ensure appropriate documentation of dispensation in the subject's medical record.

Once a subject completes the study, or if a subject is discontinued early from the study, the Investigator or designee must access the IWRS to document discontinuation of the subject from participation in the study.

7.2.2 Selection and Timing of Dose and Administration

Study drug (zavegepant or matching placebo) will be assigned via the IWRS system. There are no dose adjustments in this study and subjects will receive wallets as outlined in Table 1. Subjects will be dispensed study drug at the Baseline (Randomization) Visit, and the subjects will be instructed that they must take 4 or 8 capsules of study drug (depending on randomized treatment group assignment) every calendar day, regardless of whether they have a migraine on that day. This is the scheduled dosing regimen for the 12-week DBT Phase.

Zavegepant oral soft gelatin capsules should be taken fasting, at least 1 hour before breakfast/first meal of the day (and at least 4 hours after the previous meal).

Scheduled visit for Week 4 and Week 8 – subjects should not dose until they arrive at the study site and will take study drug with site staff to assess PK outlined in Table 1. PK will be drawn predose and at least 1 hour postdose; exact time of PK collection relative to the dose will be documented. At these visits, subjects should fast for the duration of PK assessments. Date and time of last meal will be collected (regardless of fasting status).

Subjects who complete 12 weeks of the DBT Phase may continue to take their assigned dose, either zavegepant 100 mg or 200 mg, in the OLE Phase for 52 weeks.

During the DBT or OLE Phase, if the subject has a migraine when they have *already taken study drug for the day*, the subject can take their acute migraine medication in accordance with protocol restrictions (see Section 5.5.2). Subjects **must** be instructed that they CANNOT

take more than what their randomization assignment allows (4 (four) capsules, or 8 (eight) capsules of study drug every day).

7.2.3 Dose Modifications

There will be no dose adjustments in this study.

7.3 Blinding and Unblinding

Blinding is critical to the integrity of this clinical study. However, in the event of a medical emergency or pregnancy in an individual subject, in which knowledge of the investigational product is critical to the subject's management, the blind for that subject may be broken by the treating physician.

Before breaking the blind of an individual subject's treatment, the Investigator should have determined that the information is necessary, (i.e., that it will alter the subject's immediate management). In many cases, particularly when the emergency is clearly not investigational product related, the problem may be properly managed by assuming that the subject is receiving active product without the need for unblinding.

In cases of accidental unblinding, contact the Medical Monitor and ensure every attempt is made to preserve the blind for remaining site personnel.

7.4 Treatment Compliance

Responsible study personnel will dispense the study drug. Subjects should finish a wallet blister of study drug before starting a new wallet. Accountability and compliance verification should be documented in the subject's study records.

Subjects must be counseled on the importance of taking the study drug as directed (see Section 7.2.2). Treatment compliance should be completed by a thorough review of returned study drug. Treatment compliance should be assessed by site staff at each study visit. Discrepancies, review of study drug and information provided by subject must be documented in the source record. Investigators should inform subjects that involuntary termination from the study will occur in cases where non-compliance is identified. Study staff should contact a subject in between the study visits if the subject demonstrates non-compliance with the eDiary and document the contact in the source, to identify potential lost to follow-up subjects as early as possible.

Investigators must monitor subjects for possible cases of abuse of study drug (subjects taking study drug for non-therapeutic purposes, e.g., for psychoactive effects such as high or euphoria). Investigators should also assess study drug accountability discrepancies (e.g., missing study drug, loss of drug, or non-compliance cases in which more study drug was used, as compared to expected). Investigators should obtain more information and explanation from subjects when there are study drug accountability discrepancies. See Section 8.1.1.

Cases of potential study drug abuse or overdose (including cases of non-compliance with study drug dosing instructions or subjects who discontinue treatment without returning study drug) should be documented in the source record and reported as an AE or SAE as appropriate. Overdose is defined in Section 8.3. Dosing errors (e.g., accidentally taking over the assigned number of soft gelatin capsules in one calendar day) should be reported as deviations.

7.5 **Destruction and Return of Study Drug**

All unused and/or partially used study drug can be sent back to the drug depot for destruction only after being inspected and reconciled by the responsible Study monitor or the sponsor's designee. If it is site policy to destroy study drug on site, it is the Investigator's responsibility to ensure that arrangements have been made for the disposal, procedures for proper disposal have been established according to the applicable regulations, guidelines and institutional procedures, and appropriate records of the disposal have been documented.

8 ADVERSE EVENTS

An Adverse Event (AE) is defined as any new untoward medical occurrence or worsening of a pre-existing medical condition in a subject or clinical investigation subject administered an investigational (medicinal) product and that does not necessarily have a causal relationship with this treatment. An AE can therefore be any unfavorable and unintended sign (including an abnormal laboratory finding, for example) or symptom, or any disease temporally associated with the use of the investigational product, whether or not considered related to the investigational product.

Adverse events can be spontaneously reported or elicited during an open-ended questioning, examination, or evaluation of a subject. In order to prevent reporting bias, subjects should not be questioned regarding the specific occurrence of one or more AEs.

If a specific diagnosis or syndrome is identified by the Investigator, this should be recorded as the AE, rather than recording (as separate AEs) the individual signs/symptoms or clinically significant laboratory abnormalities known to be associated with and considered by the Investigator to be a component of, the disease/syndrome.

Definition of terms related to all Adverse Events (serious and non-serious):

Mild: Is usually transient and may require only minimal treatment or therapeutic intervention. The event does not generally interfere with usual activities of daily living.

Moderate: Is usually alleviated with additional specific therapeutic intervention. The event interferes with usual activities of daily living, causing discomfort, but poses no significant or permanent risk of harm to the subject.

Severe: Interrupts usual activities of daily living, significantly affects clinical status, or may require intensive therapeutic intervention.

Life threatening: An AE is life threatening if the subject was at immediate risk of death from the event as it occurred, i.e., it does not include a reaction that if it had occurred in a more serious form might have caused death. For example, drug-induced hepatitis that resolved without evidence of hepatic failure would not be considered life threatening even though drug-induced hepatitis can be fatal.

Hospitalization: AEs requiring hospitalization should be considered SAEs. Hospitalization for elective surgery or routine clinical procedures that are not the result of AE (e.g., elective surgery for a pre-existing condition that has not worsened) need not be considered AEs or SAEs. If anything untoward is reported during the procedure, that occurrence must be reported as an AE, either 'serious' or 'non-serious' according to the usual criteria.

Assessment for Determining Relationship of AE to Study Drug:

The relatedness of each AE to study drug must be classified based on medical judgement and according to the following categories. The definitions are as follows:

Related: This category applies to AEs that are considered, with a high degree of certainty, to be related to the study drug. An AE may be considered related when it follows a temporal sequence from the administration of study drug, it cannot reasonably be explained by the known characteristics of the subject's clinical state, environment, or toxic factors, or other modes of therapy administered to the subject. An AE may be considered related when it follows a known pattern of response to the study drug, or if the AE reappears upon rechallenge.

Possibly related (**non-serious AEs only**): This category applies to AEs that are considered to have an unlikely connection to study drug, but a relationship cannot be ruled out with certainty.

Unlikely related (**non-serious AEs only**): This category applies to AEs that do not follow a reasonable temporal sequence from the administration of the study drug. The AE may readily have been produced by the subject's clinical state, environmental or toxic factors, or other modes of therapy administered to the subject.

Unrelated: This category applies to AEs that are considered with a high degree of certainty to be due only to extraneous causes (e.g., subject's clinical state, environment, toxic factors, disease under study, etc.) and does not meet the criteria of other categories above.

There are two types of adverse events, Serious Adverse Events (SAE) and Non-Serious Adverse Events (AEs).

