#### 6.4.1.2 AE Overviews

An AE overview frequency table displays the following categories without SOC and PT: any AE; AE related to study drug; AE leading to study drug discontinuation; SAE; SAE related to study drug; medication-overuse headache AE; hepatic-related AE; hepatic-related AE leading to study drug discontinuation; potential drug abuse AE; cardiovascular AE; and suicidality AE.

AE overview frequency tables are produced for the following safety analysis periods and analysis sets:

- On-DBT for the DBT safety analysis set
- Post-DBT pre-OL zavegepant for the interim safety analysis set
- On-OL zavegepant for the OL zavegepant safety analysis set
- On-DB or OL zavegepant for the DB or OL zavegepant safety analysis set
- Follow-up for the follow-up safety analysis set.

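### The two causality categories open to SAEs each require a high degree of certainty, so an SAE of uncertain cause fits neither and the 'SAE related to study drug' row depends on how sites force the choice

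*Protocol*

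**What the plan says.** Protocol Section 8 makes classification compulsory: "The relatedness of each AE to study drug must be classified based on medical judgement and according to the following categories". Four categories follow.

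- 'Related' covers events "considered, with a high degree of certainty, to be related to the study drug". Two permissive sentences then describe when an event may be placed here.
- The heading of the second category begins "Possibly related (non-serious AEs only". It covers events "considered to have an unlikely connection to study drug, but a relationship cannot be ruled out with certainty".
- The heading of the third begins "Unlikely related (non-serious AEs only". It covers events without a reasonable time relation to dosing.
- 'Unrelated' covers events "considered with a high degree of certainty to be due only to extraneous causes", provided that no other category's criteria are met.

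SAP Section 6.4.1.2 defines an AE overview table whose rows include "SAE; SAE related to study drug; medication-overuse headache AE". The table is produced for five combinations of analysis period and analysis set. SAP Sections 6.4.1.3 and 6.4.1.4 add tables of drug-related AEs by worst intensity on double-blind and open-label treatment. SAP Section 6.4.1 leaves the analysis definition of a related AE to the Core SAP, which is not among the documents.

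**The concern.** A two-level scale for SAEs is sound if the levels are complements, so that whatever is not one is the other. These two sit at opposite ends, and nothing lies between them. The one category written for a relationship that cannot be excluded is closed to SAEs. An investigator with a doubtful SAE must still pick a box, and the choice will rest on local habit rather than on a rule.

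At stake is the meaning of one planned row and of the SAE contribution to the related-AE tables. A reader of the report would take the number of related SAEs as a finding about the drug, when part of it may reflect how sites resolved a gap in the scale.

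The protocol itself produces SAEs that can fall in the gap. Under Sections 8.1.1 and 8.4, potential drug-induced liver injury is reported as an SAE on laboratory criteria plus the absence of another immediately apparent cause. That describes suspicion of the drug, which need not amount to high certainty. Secondary objectives 8 and 9 concern the liver.

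**Working it through.** The documents state no figure for related SAEs, so there is none to reproduce. The check is whether the categories cover every case.

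**Step 1: categories open to each type of event (Protocol Section 8).**

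| Category | Non-serious AE | SAE | Condition |
|---|---|---|---|
| Related | open | open | high certainty that the drug is the cause |
| Possibly related | open | closed | connection unlikely but not excluded |
| Unlikely related | open | closed | no reasonable time relation |
| Unrelated | open | open | high certainty of other causes only, and no other category's criteria met |

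**Step 2: place an SAE of uncertain cause.** Suppose the investigator thinks the drug may have contributed and cannot say more. 'Related' fails, because the certainty is missing. 'Unrelated' fails on the same ground, and also because the investigator cannot say that other causes alone explain the event. 'Possibly related', where "but a relationship cannot be ruled out with certainty", is the nearest description but is not available.

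**Step 3: look for a default rule.** Sections 8.1.1 and 8.1.2 say what to do when seriousness, or whether a hospitalization occurred, is in doubt: treat the event as serious and report it. No matching rule exists for doubt about causality. Section 8.1.2 does ask for a narrative comment when an SAE is thought unrelated to the drug but linked to study conditions. That is a different question.

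**Step 4: effect on the row.** Protocol Section 9.3.2 counts subjects. In one column of the overview table, let r be the subjects with at least one SAE that meets 'Related', and k the subjects with no such SAE but at least one of uncertain cause.

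- All uncertain SAEs put under 'Unrelated': row = r.
- All put under 'Related': row = r + k.
- Width of the range: (r + k) − r = k.

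Neither r nor k is in the documents. If k is 0 the gap has no effect.

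**Step 5: which outputs use causality.**

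- Affected: the related-SAE row, and the related-AE tables, which combine a two-level scale for SAEs with a four-level scale for other events.
- Possibly affected: SAE reports after Follow-up Week 8, which Protocol Section 8.1.2 ties to a belief that the event is related to drug or procedures. That trigger does not mention high certainty.
- Unaffected: SAE collection up to that visit (Protocol 8.1.2), secondary endpoints 7 to 9 (Protocol 3.2), the table of all SAEs (SAP 6.4.1.3), the by-subject AE listing (SAP 6.4.1) and the SAE narratives (SAP 6.4.6).

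**The case against.** The strongest reply is that the gap is narrower in practice than on paper. Classification rests on medical judgement. The permissive sentences under 'Related' let in events that follow dosing and have no other reasonable explanation, that match a known response pattern, or that recur on rechallenge. Some doubtful SAEs, including some liver cases, could enter that way. This stands in part. But the sentences sit under the certainty condition, do not say that they replace it, and do not reach an SAE with a plausible competing cause. Sites that read them differently would classify like cases differently.

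A second reply is that the Core SAP, the SAE form or the CRF instructions may settle the matter. None of them is available here. The Core SAP could regroup recorded categories, but it cannot restore one that the protocol does not allow for SAEs.

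A third is that little depends on the row. That is correct: no endpoint, stopping rule or other decision in the documents uses the number of related SAEs, and every SAE can be examined individually. In the double-blind phase the same scale applies to zavegepant and placebo, so no differential distortion between groups is shown.

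A reader might go further and infer that related SAEs are understated because 'Unrelated' is the natural default, and that the absence of a data monitoring committee makes this worse. The documents do not support that. 'Unrelated' is at least as strict as 'Related', since it demands high certainty that only other causes are at work. Site habit is not described anywhere.

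**Conclusion.** The concern holds as a gap in the scale. For SAEs the categories are not exhaustive, no default is stated, and the gap feeds a planned row and the related-AE tables. The size is k subjects per column, unknown, with the direction also unknown. The conclusion rests on a literal reading of Protocol Section 8 and on the assumption that no unseen form or instruction changes the scale.

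It does not extend to the trial's safety assessment as a whole, because the counts of all SAEs and the secondary safety endpoints do not use causality.

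A separate, minor point is that the definition of 'Possibly related' speaks of an unlikely connection, which sits awkwardly beside 'Unlikely related'. The latter has its own time-relation criterion, so the two are not identical. Both apply to non-serious AEs only, so a reader should not count this as a further fault in the SAE row.

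**What to change.** Reword the two SAE categories as complements, for example: 'Related' means there is a reasonable possibility that study drug caused the event, and 'Unrelated' means there is no reasonable possibility. Carry the same wording into the SAE form and site instructions.

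SAP Section 1 states that the study was terminated in December 2023, so new wording cannot alter causality already recorded. For those data, footnote the related-SAE row (SAP 6.4.1.2) and the related-AE tables (SAP 6.4.1.3 and 6.4.1.4). The note should say that SAEs were judged on two levels, each defined by high certainty, with no category for an uncertain cause, and should direct readers to the table and listing of all SAEs.

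Separately, remove the reference to an unlikely connection from 'Possibly related'.

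The cost is wording and footnotes. The downside of the complementary definitions is that some more SAEs may be classed as related.
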